#### **8.3.6 Hospital stays and emergency room visits**

Hospital stays and emergency room (ER) visits will be attributed to study periods as defined in section 3.2.2 based on admission date.

The number of hospital stays per subject during the Baseline Period and during the entire Treatment Period, separately, will be summarized by treatment group. The number of hospital stays will be summarized using the categories 0, 1, 2, 3, 4, and 5 or more. The number and percentage of subjects with specific reasons for duration of hospital stays will be summarized for the duration of the Baseline Period and for the duration of the entire Treatment Period, separately, by treatment group.

Duration of hospital stays will be categorized as 0 days, 1-5 days, 6-10 days, 11-15 days, and >15 days, and summarized for the duration of the Baseline Period and the duration of the entire Treatment Period, separately, by treatment group.

An event logged on the Hospitalization/ER Visit eCRF module where ER is marked as the initial entry point will be defined as an ER visit. An ER visit with a subject transfer to an inpatient general ward will also be counted as a hospitalization. However, all other instances of ER visits (where subject transfer is not to an inpatient general ward) will not be counted as hospitalizations. Descriptive statistics for the number of ER stays during the Baseline Period and for the duration of the entire Treatment Period, will be presented, separately, by treatment group. The number of ER visits will be summarized using the categories 0, 1, 2, and 3 or more. The number and percentage of subjects with specific reasons for duration of ER visits will be summarized for the duration of the Baseline Period and the duration of the entire Treatment Period, separately, by treatment group.

The duration of each hospital stay will be calculated as the discharge date minus the admission date (Hospitalization/ER Visit Date on the eCRF) plus 1 day for hospital stays with a discharge date. Hospitalizations with either a partial admission or discharge date are ignored for the calculation of duration of hospital stay. However, such hospitalizations are counted for the number of hospital stays. The durations of hospital stays will be summed within each of the study periods defined in section 3.2.2. Subjects with no hospital stays within a study period will have a duration of 0 days for that period. Should distinct records for hospital stays overlap, then the days during the overlap will only be counted once. Similarly, this also applies for the ER visits.

All hospitalization/ER data will be listed.

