6.3 Withdrawal criteria

Subjects are free to withdraw from the study at any time, without prejudice to their continued care.

Subjects **must** be withdrawn from this study if any of the following events occur:

1. Subject experiences intolerable AEs, including clinically relevant abnormal laboratory findings that, in the opinion of the investigator, preclude further participation in the study.
2. The sponsor or a regulatory agency requests withdrawal of the subject.
3. Subject has QTc interval ≥ 500 ms that is confirmed by a cardiologist overread on any ECG.
4. Subject develops a second degree atrioventricular (AV) block while awake or develops a third degree AV block.
5. For subjects ≥ 6 years of age, subject has actual suicidal ideation since last visit as indicated by a positive response ("Yes") to either Question 4 or Question 5 of the C-SSRS. The subject should be referred immediately to a Mental Healthcare Professional and must be withdrawn from the study.

6. Subject is unwilling or unable to continue, or the parent/legal representative is unwilling or unable to allow the subject to continue in the study.
7. Investigator decides that withdrawal from further participation would be in the subject's best interest.
8. Subject experiences convulsive status epilepticus.
9. Subject uses rescue medication in excess of that permitted by the protocol.
10. In the case of liver function test (LFT) results of transaminases (AST, ALT, or both) $\geq 3x$ ULN to $< 5x$ ULN and total bilirubin $\geq 2x$ ULN or transaminases (AST, ALT, or both) $\geq 5x$ ULN, the study medication must be immediately discontinued and the subject withdrawn from the study. The LFTs will be repeated as soon as possible, and in no case > 1 week later.
11. Female subject who achieves menarche and does not practice contraception as provided in Exclusion Criteria 6 unless sexually abstinent. Subject becomes pregnant, as evidenced by a positive pregnancy test.
12. Subject needs any alteration in AED daily dose or VNS settings.

Participation in this study may be discontinued for any of the following reasons:

1. Subject has any clinically relevant change in medical or psychiatric condition (if in the opinion of the investigator, the change in condition warrants discontinuation from the study).
2. Subject requires a medication that is not permitted by the protocol.
3. Subject and/or delegated caregiver is noncompliant with study procedures or medication, in the opinion of the investigator.

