11.2 Serious adverse events

11.2.1 Definition of serious adverse event

Once it is determined that a subject experienced an AE, the seriousness of the AE must be determined. An SAE must meet 1 or more of the following criteria:

- Death
- Life-threatening

(Life-threatening does not include a reaction that might have caused death had it occurred in a more severe form.)

- Significant or persistent disability/incapacity
- Congenital anomaly/birth defect (including that occurring in a fetus)
- Important medical event that, based upon appropriate medical judgment, may jeopardize the patient or subject and may require medical or surgical intervention to prevent 1 of the other outcomes listed in the definition of serious

(Important medical events may include allergic bronchospasm requiring intensive treatment in an emergency room or at home, blood dyscrasias that do not result in inpatient hospitalization, or the development of drug dependency or drug abuse.)

- Initial inpatient hospitalization or prolongation of hospitalization

(A patient admitted to a hospital, even if he/she is released on the same day, meets the criteria for the initial inpatient hospitalization. An emergency room visit that results in admission to the hospital would also qualify for the initial inpatient hospitalization criteria. However, emergency room visits that do not result in admission to the hospital would not qualify for this criteria and, instead, should be evaluated for 1 of the other criteria in the definition of serious [eg, life-threatening adverse experience, important medical event].

Hospitalizations for reasons not associated with the occurrence of an AE [eg, preplanned surgery or elective surgery for a pre-existing condition that has not worsened or manifested in an unusual or uncharacteristic manner] do not qualify for reporting. For example, if a subject has a condition recorded on his/her medical history and later has a preplanned surgery for this condition, it is not appropriate to record the surgery or hospitalization as an SAE, since there is no AE upon which to assess the serious criteria. Please note that, if the pre-existing condition has worsened or manifested in an unusual or uncharacteristic manner, this would then qualify as an AE and, if necessary, the seriousness of the event would need to be determined.)

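### SAP 8.3.6 makes transfer to a general ward the test for counting an ER-entry event as a hospitalization, so a stay in another inpatient unit can be tabulated as 0 stays and 0 days

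*SAP*

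**What the plan says.** SAP 8.3.6 works from the hospitalization/ER module of the electronic case report form (eCRF). An event "where ER is marked as the initial entry point will be defined as an ER visit". One route then leads from ER visit to hospital stay: "An ER visit with a subject transfer to an inpatient general ward will also be counted as a hospitalization". The next sentence closes the class: "However, all other instances of ER visits (where subject transfer is not to an inpatient general ward) will not be counted as hospitalizations".

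The duration rules in the same section build on that classification. "The duration of each hospital stay will be calculated as the discharge date minus the admission date", plus 1 day. Durations are summed within each study period, and "Subjects with no hospital stays within a study period will have a duration of 0 days for that period". The table uses bands: "Duration of hospital stays will be categorized as 0 days, 1-5 days, 6-10 days, 11-15 days, and >15 days".

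The variable behind these tables is health care resource use. Protocol 4.1.3 and 9.2.2.2 and SAP 2.2.1.3 all describe it as including hospitalizations that the protocol did not foresee, and none of them mentions type of ward. SAP 3.9 states that the protocol's analyses are unchanged.

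**The concern.** The exclusion is defined by where the child is sent, not by whether the child was admitted. The parenthesis in the closing sentence makes this clear: it covers any transfer to somewhere other than a general ward, not only discharge home. A child admitted from the ER to intensive care or a specialist unit is an inpatient by ordinary usage, yet on the literal text is not counted as hospitalized.

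Two things follow. The table of hospital stays and days would be narrower than the variable named in the protocol, although SAP 3.9 declares no change. And the route of entry, rather than the inpatient care received, would decide whether days in hospital exist for the table. What is at stake is the descriptive picture of hospital burden by arm.

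**Working it through.** There is no plan figure to reproduce and no statistical calculation involved. The check applies the counting and duration rules of SAP 8.3.6 literally to a set of cases.

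Inputs from SAP 8.3.6: the definition of an ER visit (ER as initial entry point); the condition for also being a hospitalization (transfer to a general inpatient ward); the exclusion of all other ER visits; duration = discharge date − admission date + 1; 0 days where no stay is counted; the five duration bands.

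Assumed dates, for illustration only: admission on day 1, discharge on day 8, no other event for that subject in the period. The formula gives 8 − 1 + 1 = 8 days, which falls in the 6-10 day band.

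| Case | ER visits | Hospital stays | Days (band) |
|---|---|---|---|
| ER, then general ward | 1 | 1 | 8 (6-10) |
| ER, then another inpatient unit, never a general ward | 1 | 0 | 0 (0 days) |
| Same unit and dates, entry not through the ER | 0 | 1 | 8 (6-10) |
| ER, then another unit, then general ward | 1 | not settled by the text | not settled |

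The second and third rows describe identical inpatient care. They differ by 1 stay and 8 days solely because of the entry point. The fourth row is open because the SAP asks for a transfer to a general ward without saying that it must be the first transfer.

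No exception for other inpatient units appears in current SAP 8.3.6 or elsewhere in either document. The sentence is operative text; the SAP amendment log shows the same wording as the one adopted.

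**The case against.** The strongest reply is that the rule operates on a form the reader cannot see. The eCRF's transfer options are not in the documents. If the general-ward label is the form's only inpatient destination, as opposed to discharge, every inpatient transfer meets the condition and nothing is lost. This stands as a limit on size. It does not dispose of the point, because the SAP does not say so and its wording sorts events by destination.

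The second reply is that the events stay visible. An excluded stay is still counted as an ER visit by arm, still contributes to the tabulated reasons for ER visits, and is listed with all other hospitalization and ER data. That is correct.

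Third, a reader might set the rule against Protocol 11.2.1, which says "An emergency room visit that results in admission to the hospital would also qualify for the initial inpatient hospitalization criteria", and infer a contradiction. The documents do not support that. Protocol 11.2.1 defines seriousness for adverse event reporting, and the SAP does not say that the resource-use table adopts it. The two definitions can give different answers for one event, but neither binds the other, and serious adverse event reporting is unaffected.

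Fourth, a reader might infer that the rule systematically removes the most severe seizure-related admissions and keeps the milder ones, pointing to the withdrawal criterion in Protocol 6.3: "Subject experiences convulsive status epilepticus". That criterion says nothing about counting hospital stays. The exclusion reaches only ER-entry events, a child who later moves to a general ward may still count, and the documents do not show that the stays left out are the most severe. The stronger reading does not hold.

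**Conclusion.** The point holds in a limited form. Taken literally, SAP 8.3.6 leaves an ER-origin stay in a non-general inpatient unit out of the number and duration of hospital stays, unless the child reaches a general ward. The protocol variable carries no such restriction, and the same stay reached by another route is not excluded.

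For each affected subject with no other stay in the period, the effect is complete: 0 stays and 0 days in place of 1 stay and its actual length. Across the trial the size cannot be derived. Neither the number of ER admissions nor their destinations are given, and the documents are compatible with no affected stays at all. The conclusion assumes that the eCRF distinguishes a general ward from other inpatient destinations.

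Severity is minor. Health care resource use is among the other efficacy variables, for which Protocol 13.3.3 rules out statistical testing. The primary and secondary efficacy analyses and the adverse event analyses are untouched.

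**What to change.** In SAP 8.3.6, replace the two sentences on transfer with a rule such as:

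> An ER visit is also a hospitalization when the transfer recorded on the eCRF is to any inpatient unit. The eCRF transfer categories that qualify are: [list]. ER visits without inpatient admission count as ER visits only. The same classification determines duration of stay.

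The list should use the transfer categories that the eCRF already has. If it turns out that the general-ward category covers every inpatient transfer, saying so in the SAP resolves the point with no change in results. A rule based on any inpatient unit also settles the sequence of ER, another unit, then general ward.

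The cost is a sentence or two and one condition in the derivation code. Counts of hospital stays may rise slightly. Because the rule relies on existing categories, it asks for no new data collection, but it can separate destinations only as finely as the form already does.

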## **9 PHARMACOKINETICS**

### **9.1 Descriptive statistics of LCM and AED plasma concentrations**

The results of LCM and other AEDs plasma concentrations will be described by the method of descriptive statistics: arithmetic mean, SD, median, range, geometric mean, and geometric CV. The evaluations will be done based on separation by LCM maintenance dose level, and repeated by LCM maintenance dose level and age group.

Summarization of PK data relative to time after dose will be performed for the overall group and separated by AED therapy and possibly age groups.

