8.1.1 Baseline Period: Visit 1 (Week -8) (Screening)

At Visit 1, subjects will be evaluated for their suitability for enrollment. It is acceptable for this visit to be conducted on more than 1 day; however, all results of Visit 1 assessments should be available before T1. Prior to the conduct of any study-related procedures, a complete explanation (both verbal and written) of the nature and purpose of the study will be given to the subject by the investigator (or designee). The subject or parent/legal representative is required to sign and date the IRB/IEC-approved informed consent if he/she decides to participate in the study.

The subject's eligibility for the study will be determined on the basis of the inclusion/exclusion criteria, signature of an informed consent prior to any study-related procedures or evaluations, and the results of the following pretreatment assessments (for further details of the assessments and the required procedures and methods, please refer to Section 9, Section 10, and Section 11 of this protocol):

- Medical history
- Seizure history
- Concomitant medications
- Concomitant AEDs
- VNS assessment (for subjects with an implanted VNS device)
- Physical examination (complete)
- Tanner Stage assessment
- Vital signs (BP and pulse rate, including orthostatic assessments)
- Body weight assessment
- Height assessment
- Head circumference
- Neurological examination (complete)

- 12-lead ECG (2 interpretable recordings [20 to 30 minutes apart] to be performed prior to any blood draws and vital signs assessment and ,if possible, with the subject in the supine position for approximately 5 minutes preceding the recordings and during the recordings)
- Blood sample for clinical chemistry and hematology
- Urine sample for urinalysis (for subjects ≥ 5 years of age)
- Serum pregnancy test (for females of childbearing potential)
- Blood sample for measurement of concomitant AED plasma concentrations
- Blood sample for measurement of LCM plasma concentration
- C-SSRS (for subjects ≥ 6 years of age)
- Contact IXRS to obtain unique subject identification number
- Dispense subject diary
- AE reporting
- Assessments of subject's candidacy for epilepsy surgery/VNS
- Health care resource use

The subject will be scheduled to return to the clinic as specified in [Table 5-1](#). The morning of the next clinic visit, the subject should take concomitant AEDs at the usual time(s).

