At each clinic visit and telephone contact, the investigator, in conjunction with the subject and/or parent(s)/legal representative(s), will decide how to proceed with study medication dosing based on tolerability (including vital signs, body weight, 12-lead ECG, and AE reporting, as applicable to the type of contact). If the withdrawal of study medication is required during the Titration Period, the subject will enter the blinded Taper Period (Section 8.5).

8.2.1 Titration Period: Telephone Contact 2 (Week 1), Telephone Contact 3 (Week 3), and Telephone Contact 4 (Week 5)

During the Titration Period telephone contacts (Telephone Contact 2, Telephone Contact 3, and Telephone Contact 4), the following assessments will be performed:

- Concomitant medications
- Concomitant AEDs
- Reminder to complete subject diary on a daily basis
- Review withdrawal criteria
- AE reporting

8.2.2 Titration Period: Visit 3 (Week 2), Visit 4 (Week 4), and Visit 5 (Week 6)

During the Titration Period clinic visits (Visit 3, Visit 4, and Visit 5), the following assessments will be performed:

- Concomitant medications
- Concomitant AEDs
- VNS assessment (for subjects with an implanted VNS device)
- Physical examination (brief)
- Vital signs (BP and pulse rate, including orthostatic assessments)
- Body weight assessment
- Neurological examination (brief)
- 12-lead ECG (2 interpretable recordings [20 to 30 minutes apart] to be performed prior to any blood draws and vital signs assessment and, if possible, with the subject in the supine position for approximately 5 minutes preceding the recordings and during the recordings)
- Blood sample for clinical chemistry and hematology (Visit 4 and Visit 5 only)
- Urine sample for urinalysis (for subjects ≥ 5 years of age) (Visit 4 and Visit 5 only)
- Serum pregnancy test (for females of childbearing potential) (Visit 4 and Visit 5 only)
- Urine pregnancy test (for females of childbearing potential) (Visit 3 only)
- Blood sample for determination of concomitant AED plasma concentration (Visit 5 only)

- Blood sample for determination of LCM plasma concentration (Visit 5 only)
- C-SSRS (for subjects ≥ 6 years of age)
- Achenbach CBCL (same version used at Visit 2) (Visit 5 only)
- Contact IXRS
- Dispense study medication
- Study medication return
- Reminder to complete subject diary on a daily basis
- Review withdrawal criteria
- AE reporting
- Health care resource use

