10 ASSESSMENT OF PHARMACOKINETIC/ PHARMACODYNAMIC VARIABLE(S)

Blood samples for the determination of LCM and concomitant AED plasma concentrations will be collected according to the tabular schedules of study procedures (see Section 5.2). In each case, the time the subject took the most recent dose of study medication and the time of blood sampling must be recorded. Actual sampling times will be recorded in the CRF to the minute.

Details of plasma sample collection and processing, sample labeling, and shipment will be provided in the laboratory manual.

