13.4.2 Pharmacokinetic analyses

13.4.2.1 Descriptive statistics of LCM and AED plasma concentrations

The results of LCM and other AEDs plasma concentrations will be described by the method of descriptive statistics: arithmetic mean, SD, median, range, geometric mean, and geometric coefficient of variation. The evaluations will be done based on separation by LCM dose level and study period.

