### **2.2.3 Pharmacokinetic variables**

Plasma concentrations of LCM and concomitant AEDs will be obtained in order to:

- Develop a population PK model of LCM

- Investigate the effect of LCM on the steady-state plasma concentrations of concomitant AEDs
- Investigate the correlation between LCM plasma concentrations and efficacy or safety

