### **3.9 Changes to protocol-defined analyses**

There are no changes to analyses specified in the protocol.

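### SAP 9.1 replaces the protocol's study-period split of plasma concentrations with maintenance dose level, undeclared, so no specified summary compares concomitant AED levels before and during lacosamide

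*SAP*

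**What the plan says.** The aim appears in the same words in Protocol 4.3 and SAP 2.2.3: "Investigate the effect of LCM on the steady-state plasma concentrations of concomitant AEDs".

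The sampling supports it. Protocol 8.1.1 lists, at Visit 1 and before any study drug, "Blood sample for measurement of concomitant AED plasma concentrations". AED and LCM samples follow at Visit 5 (Protocol 8.2.2), Visit 8 (8.3.3), TV4 (8.4.2) and any Early Termination Visit (8.8).

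The documents differ on how the results are broken down:

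- Protocol 13.4.2.1: "The evaluations will be done based on separation by LCM dose level and study period".
- SAP 9.1: "The evaluations will be done based on separation by LCM maintenance dose level, and repeated by LCM maintenance dose level and age group".

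SAP 9.1 adds a second summary: "Summarization of PK data relative to time after dose will be performed for the overall group and separated by AED therapy and possibly age groups". This is not by period or visit either. SAP 3.9 states: "There are no changes to analyses specified in the protocol".

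**The concern.** An effect of LCM on an AED level is seen by comparing levels without LCM and levels with it. The protocol's split by study period keeps Visit 1 apart from the samples taken on treatment. The SAP's grouping variable does not vary within a subject, so it cannot do this.

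At stake is a stated purpose of repeated blood sampling in children. As the SAP is written, no prespecified table serves that purpose, and a reader relying on SAP 3.9 would not know that the breakdown had changed. Any before/during comparison would then have to be devised outside the SAP, possibly after unblinding.

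**Working it through.** The plan gives no figure to reproduce. The check is mainly a comparison of the texts, followed by a small illustration.

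**1. Does the SAP's variable separate exposed from unexposed samples?** Protocol 7.2.2 keeps the dose stable throughout Maintenance, so each subject has one maintenance dose level. Visit 1, Visit 5, Visit 8 and TV4 samples from one subject therefore carry the same label. They are not separated.

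**2. Does every sampled subject have a label?**
- Placebo subjects have no LCM maintenance dose, and SAP 9.1 does not say whether placebo is a level. Those entering Transition are on LCM by TV4 (Protocol 7.2.3, Table 7-4).
- Subjects who stop during Titration give an early-termination sample (Protocol 8.8) but never have a maintenance dose.

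**3. Does another SAP section supply the comparison?** SAP 9.2 models LCM concentrations only. SAP 9.3 relates LCM to seizure counts. The second summary in 9.1 is by time after dose and AED therapy. None compares AED levels before and during LCM.

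**4. Illustration: what if visits were pooled and placebo shown as a group?** SAP 9.1 does not say this will be done. Let r be the true ratio of an AED level on LCM to its level off LCM. The documents give no r; values from 0.75 to 1.25 are assumed. Set the off-LCM level to 1, with one sample per scheduled visit and the same r at every exposed visit.

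Visits 1, 5 and 8:
- LCM arm mean = (1 + 2r)/3; placebo mean = 1.
- Difference = (2/3)(r − 1).

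Visits 1, 5, 8 and TV4:
- LCM arm mean = (1 + 3r)/4; placebo mean = (3 + r)/4.
- Difference = (1/2)(r − 1).

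| r | LCM vs placebo, without TV4 | LCM vs placebo, with TV4 |
|---|---|---|
| 0.75 | 0.833 vs 1.000 | 0.812 vs 0.938 |
| 0.80 | 0.867 vs 1.000 | 0.850 vs 0.950 |
| 0.90 | 0.933 vs 1.000 | 0.925 vs 0.975 |
| 1.10 | 1.067 vs 1.000 | 1.075 vs 1.025 |
| 1.25 | 1.167 vs 1.000 | 1.188 vs 1.062 |

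The share retained is 2/3 or 1/2 whatever r is. Geometric means behave in the same way: at r = 0.80 the arm ratio is 0.80^(2/3) = 0.862 without TV4, and 0.80^(3/4) / 0.80^(1/4) = 0.894 with it. Split by visit, Visit 5 or Visit 8 against Visit 1 in the LCM arm gives r itself.

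**The case against.** The strongest reply is that this is a drafting gap and little more. The protocol still requires the period split and SAP 3.9 disclaims any departure, so a programmer could simply follow the protocol. SAP 3.1 provides listings of all data sorted by visit where applicable. SAP 9.1 omits the split without ordering pooling. Maintenance dose level might even mean that only samples taken on the maintenance dose are summarised. If placebo were then shown alongside, the arms could be compared without dilution. The protocol plans only descriptive PK statistics, with no paired ratio and no placebo contrast, so their absence is not the SAP's doing. The AED question is a purpose of sampling in Protocol 4.3 and is not among the objectives in Protocol 3.

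Most of this stands, and it limits the point. It does not remove it. Restricting the table to maintenance-dose samples would leave out Visit 1, so the before/during comparison would still be missing; and SAP 9.1 states neither that restriction nor a placebo column. Two documents that specify different breakdowns, one of them saying nothing has changed, need reconciling.

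A reader might infer three stronger things that the documents do not support:

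- *That mean LCM concentrations would be understated by a quarter because Visit 1 zeros are averaged in.* SAP 9.1 calls for geometric means and geometric CVs, which zeros do not allow, and its other summary is relative to time after dose. Nothing suggests that Visit 1 values enter an LCM mean.
- *That AED levels cannot be placed between trough and peak.* Protocol 10 does say that "the time the subject took the most recent dose of study medication and the time of blood sampling must be recorded" and names no AED dose time. But it leaves collection details to a laboratory manual that is not available here, nor is the case report form. AED regimens must also be stable and taken at the usual times on clinic mornings.
- *That the SAP pools exposed and unexposed samples.* It is silent on this.

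**Conclusion.** The point holds as a conflict between the documents and a gap in the SAP. SAP 9.1 drops the protocol's study-period split without declaring it. Its replacement cannot separate samples within a subject and does not fit two groups of sampled subjects. No SAP summary as specified delivers the AED comparison that both documents give as an aim.

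It would go too far to conclude that the aim cannot be met. The pre-exposure and on-treatment samples are planned, there is a concurrent placebo arm up to Visit 8, and the listings allow the comparison to be made later. What is missing is its prespecification.

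The retained shares of 2/3 and 1/2 are conditional. They assume pooled visits, a placebo group, complete sampling with equal weights, and one common effect at every exposed visit, including TV4, where placebo subjects are at the end of the Table 7-4 schedule. They show the direction, towards no apparent interaction, and the possible size. They are not properties of the plan.

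No efficacy conclusion, error rate or power depends on this. It is worth correcting because the question is stated and the blood is drawn for it.

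**What to change.** In SAP 9.1:

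- Tabulate LCM and each AED by treatment group and study period or visit (Visit 1, Visit 5, Visit 8/Early Termination), with placebo shown as a group and early-termination samples identified by the period in which they were taken.
- Keep TV4 in a separate table, classed by the drug actually being taken.
- For each AED, add the descriptive within-subject ratio of Visit 5 to Visit 1 and of Visit 8 to Visit 1, by treatment group, in subjects with paired samples.

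The first item restores the protocol's split. The ratios go a step beyond the protocol but remain descriptive and answer the question directly. The maintenance-dose and age-group breakdowns can stay as additional tables.

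If the sponsor prefers the present grouping, SAP 3.9 should declare the departure and say how the AED aim will be addressed.

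The cost is SAP wording and a few more tables, with no extra samples. The downside is small numbers for each individual AED.
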